5.3.1 Case report form

No information related to patient identity (initials, full date of birth, etc) will be entered in the eCRF.

The following information will be recorded in the eCRF using the data available in the medical file or collected during the visit (as part of the routine patient management):

- » Date of the inclusion visit (the only study visit) and type of visit (outpatient visit, day hospital, in-patient hospitalisation).
- » Patient eligibility criteria.
- » Demographic data:
 - Year of birth, gender,
 - Smoking status (smoker, never smoker),
- » Clinical data:
 - Height, weight (at diagnosis, at the inclusion visit)
 - Medical history:
 - significant past and current comorbidities (e.g. diabetes, high blood pressure, dyslipidaemia, osteoporosis, neuropsychiatric disorders,

depression, insomnia, serious infection disease, parasitic diseases, cancer, stroke, coronary artery disease, ischemic cardiopathy, peripheral artery diseases, adrenal insufficiency, cataract, glaucoma, gastro-intestinal ulcer, digestive perforation, other significant history),

- start and stop date (month, year) of comorbidities
- Comorbidities related to GCs for GCA patients (i.e. which appeared or worsened during GCs treatment according to the investigator judgement).

» GCA patient journey:

- Incident or prevalent patient:
 - Newly diagnosed (i.e. incident) patient will be defined as patient with GCA diagnosis within the last 6 weeks before visit
 - Not newly diagnosed (i.e. prevalent) patients will be defined as patient with GCA diagnosis more than 6 weeks before visit
- Date of initial diagnosis
- Date of GCA signs/symptoms (month and year)
- Physician(s) who referred the patient (General Practitioner, Ophthalmologists, Neurologist, Emergency, Internist, Rheumatologist, Other).

» GCA characteristics:

- Initial presentation at diagnosis and inclusion visit:
 - Cranial (localized headache, scalp tenderness, temporal artery tenderness or decreased pulsation, ischemia-related vision impairment / loss, mouth or jaw pain upon mastication, stroke or transient ischaemic attack (TIA), other)
 - PMR (morning stiffness and/or pain in the shoulder and/or pelvic girdles, inflammatory arthromyalgia, peripheral arthritis, other)
 - Extracranial (large-vessel GCA i.e. thoracic or abdominal aortic aneurysm, myocardial infarction, dilatation, limb claudication, subclavian stenosis, other)
 - ESR/CRP
 - General signs: fever, weight loss (%), health status modification

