The EQ5D-3L consists of five questions relating to five dimensions of health. Respondents indicate which of a possible three statements best describe their current health state for each dimension. Each dimension has 3 levels: no problems, some problems, extreme problems. Respondents are asked to repeat this process for the five dimensions by indicating one level for each dimension, giving rise to scores ranging from 1 to 3, with scores of 3 on each dimension indicating the most severe impairment. Binary variables will be computed for each dimension dichotomising the levels into 'No problems' (level 1) and 'Problems' (levels 2 and 3). Perceived current health state will be measured by asking respondents to indicate their current health state on a VAS with endpoints labelled 0 'Worst imaginable health state' and 100 'Best imaginable health state. The score for each item of EQ5D-3L will be presented (in qualitative variable at 2 and 3 modalities for 5 dimensions and in quantitative for VAS).

» FACIT-Fatigue

FACIT-Fatigue is a patient-reported rating scale consisting of 13 items that yields a summed total score ranging between 0 and 52 (52= less fatigue).

The score for each items of FACIT-Fatigue will be presented (in qualitative variable) as well as the total score (quantitative variable).

Description of physician and patient characteristics

» Description of physicians

The analysed data will be recorded by the physician in the eCRF.

The population of physicians in the study will be described overall, in terms of demographic parameters (geographic location, number of years of practice, year of medical school graduation), medical specialty, status of the health institution (public hospital, private hospital, both hospital and office-based, other) and number of GCA diagnosis within the previous year.

» Description of patients

Demographic data (age, gender, smoking status) and body mass index will be described overall and by type of physician who follows the patient.

Current and past comorbidities of GCA patients (significant past and concomitant diseases) will be coded by the medical dictionary MedDRA®. They will be described overall and by type of physician who follows the patient.

Treatments will be coded using the WHO Drug medicine dictionary (ATC codes). They will be described overall and by type of physician who follows the patient.

7.2.4 *Schedule for data analysis*

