5.5.4.2 Description of patients

The following patients' characteristics will be described overall and by type of physician who follows the patient:

- Type of the patient's visit (Outpatient visit/Day hospital/ In-patient hospitalization)
- Age (years) as quantitative variable and in classes ([50 ; 70[/ ≥ 70) ([APPENDIX](#))
- Gender
- Weight at diagnosis (kg)
- Weight at inclusion (kg)
- Height at diagnosis (cm)
- Body mass index (BMI) (kg/m²) at diagnosis ([APPENDIX](#))
- BMI in classes (kg/m²) (<18.5 / [18.5 ; 25[/ [25.0 ; 30[/ ≥ 30) at diagnosis
- Smoking status (Smoker/ Former smoker/ Non-smoker ever / Unknown)
- Significant medical and surgical history and comorbidities (excluding those related / aggravated by the use of glucocorticoids according to the investigator's judgment and complications related to GCA (Horton) according to the investigator's judgment

- Significant medical and surgical history and comorbidities overall by MedDRA System Organ Class (SOC) and Preferred Term (PT)
- Significant medical and surgical history and comorbidities presented before the GCA (HORTON) diagnosis
- Significant medical and surgical history and comorbidities with ongoing specific treatment(s)

A listing of other significant medical and surgical history and comorbidities (excluding those related / aggravated by the use of glucocorticoids according to the investigator's judgment and complications related to GCA (Horton) according to the investigator's judgment) will be presented.

- Treatments administered by the patients at/after diagnosis of GCA (Horton)
 - Proportion of patients taking at least one treatment of Antiplatelets
 - Proportion of patients taking at least one treatment of Statins
 - Proportion of patients taking at least one treatment of Antiosteoporotic
 - Proportion of patients taking at least one treatment of Antihypertensives
 - Proportion of patients taking at least one treatment of Antidiabetics
 - Proportion of patients taking at least one treatment of Inhibitors of the proton pump
 - Proportion of patients taking at least one treatment of Hypnotics
 - Proportion of patients taking at least one treatment of Antidepressants
 - Proportion of patients taking at least one other treatment

- Concomitant treatments administered by the patients at diagnosis of GCA (Horton)
 - Proportion of patients taking at least one treatment of Antiplatelets
 - Proportion of patients taking at least one treatment of Statins

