9.3 Analyses of secondary objectives

9.3.1 Description of comorbidities related to GCs and associated treatment

Table 12 - Efficacy analysis – Comorbidities related/ aggravated by the use of GCs according to the investigator’s judgment by MedDRA SOC and PT – Analysis population (N=XX)

System Organ Class	Preferred Term	Total (N=XX)	
		# Patients (%)	# MHs (%)
Patients with at least one comorbidity related/aggravated by GCs use			
Number of medical and surgical history and comorbidities			
SOC1			
	PT1.1		
	PT1.2		
	...		
SOC2			
	PT2.1		
	PT2.2		
	...		
...			

Study: CHUGAI-ARTEMIS - Edition date: DDMMYY

Pgm : EFFICACYCOM.SAS

Patients (%): Number of patients (percentages with number of patients as reference)

MHs (%): Number of medical/surgical history and comorbidities (multiple occurrences of the same medical/ surgical history or comorbidities in one patient are counted multiple times) (percentages with number of medical / surgical history events or comorbidities as reference)

The same table will be presented according to the type of physicians who follows the patient.

Table 13 - Efficacy analysis – Ongoing specific treatments for patients with comorbidities related to the use of GCs - Patients with comorbidities related to the use of GCs (N=XX)

Parameter	Statistics	Total (N=XX)
Patients with at least one ongoing specific treatments for comorbidities related to the use of GCs		
No	n(%)	
Yes	n(%)	
	Filled, n(%)	
	Missing, n(%)	

The percentages are calculated compared to filled data

STUDY : CHUGAI-ARTEMIS - Edition date: DDMMYY

Pgm : EFFICACYCOM.SAS

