Kinetics for which a corticotherapy for GCA (Horton) care has restarted after the kinetic No Yes	n(%) n(%) Filled, n(%) Missing, n(%)	

IV : Intravenous PO : Per Oral

The percentages are calculated compared to filled data

STUDY : CHUGAI-ARTEMIS - Edition date: DDMMYY

Pgm : EFFICACY\GCA.SAS

Table 20 - Efficacy analysis – Clinical Form - GCA complications - Analysis population (N=XX)

Parameter	Statistics	Total (N=XX)
Patient with at least one GCA complication		
No	n(%)	
Yes	n(%) Filled, n(%) Missing, n(%)	
If yes, Patient with ongoing specific treatment(s) for GCA complications		
No	n(%)	
Yes	n(%) Filled, n(%) Missing, n(%)	

The percentages are calculated compared to filled data
STUDY : CHUGAI-ARTEMIS - Edition date: DDMMYY
Pgm : EFFICACY\GCA.SAS

Table 21 - Efficacy analysis – Complications related to GCA according to the investigator's judgment by MedDRA SOC and PT – Analysis population (N=XX)

System Organ Class	Preferred Term	Total (N=XX)	
		# Patients (%)	# Comps (%)
Patients with at least one complication related to GCA			
Number of complications related to GCA			
SOC1			
	PT1.1		
	PT1.2		
	...		
SOC2			
	PT2.1		
	PT2.2		
	...		
...			

Study: CHUGAI-ARTEMIS - Edition date: DDMMYY
Pgm : EFFICACY\COM.SAS

Patients (%): Number of patients (percentages with number of patients as reference)

Comps (%): Number of complications (multiple occurrences of the same complication in one patient are counted multiple times) (percentages with number of complications as reference)

This table will be presented also by type of physicians who follows the patient.

Table 22 - Efficacy analysis – Univariate analysis* of the effect of the patients characteristics on the relapse (outcome variable : at least one relapse / no relapse) – Analysis population (N=XX)

Parameter	OR [CI 95%]	pvalue
Age in classes		x.xxxx
[50 – 70[(reference)	1.00	
≥ 70 years	X.XX [X.XX ; X.XX]	
Gender		...
Male (reference)	...	
Female	...	
BMI in classes (kg/m²)		
Normal (BMI between [18.5-25]) (reference)		
Under weight (BMI <18.5)		
Over weight (BMI between [25.0 ; 30])		
Obesity (BMI ≥ 30)		
Smoking status		
Non-smoker ever (reference)		
Former smoker		
Smoker		
Unknown		
Type of patient		
Prevalent (reference)		
Incident		
Physician who referred the patient		
General practitioner (reference)		
Ophthalmologist		
Neurologist		
Emergency		
Internist		

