	Filled, n(%) Missing, n(%)	
Smoking status		
Smoker	n(%)	
Former smoker	n(%)	
Non-smoker ever	n(%)	
Unknown	n(%)	
	Filled, n(%) Missing, n(%)	

The percentages are calculated compared to filled data
 STUDY : CHUGAI-ARTEMIS - Edition date: DDMMYY
 Pgm : DESCR\DEMO.SAS

This table will be presented by type of physician who follows the patient.

Table 34 - Descriptive analysis – Significant medical and surgical history and comorbidities (excluding those related to the use of GCs and complications related to GCA) overall by MedDRA SOC and PT – Analysis population (N=XX)

System Organ Class	Preferred Term	Total (N=XX)	
		# Patients (%)	# MHs (%)
Patients with at least one significant comorbidity			
Number of medical and surgical history and comorbidities			
SOC1			
	PT1.1		
	PT1.2		
	...		
SOC2			
	PT2.1		
	PT2.2		
	...		
...			

Study: CHUGAI-ARTEMIS - Edition date: DDMMYY

Pgm : DESCRIDEMO.SAS

Patients (%): Number of patients (percentages with number of patients as reference)

MHs (%): Number of medical history and comorbidities (multiple occurrences of the same medical history in one patient are counted multiple times) (percentages with number of medical history events as reference)

The same table will be presented for significant medical and surgical history and comorbidities presented before the GCA (Horton) diagnosis and those with ongoing specific treatment(s) overall and according to the type of physicians who follows the patient.

Listing 12 : Other significant medical and surgical history and comorbidities (excluding complicated related to GCA and to the use of GCs) (N= XX)

Patient ID	Newly /not newly diagnosed patient	Type of diagnosis	Physician who follows the patient	Specification of other comorbidities	Start date	Date of inclusion	Present before GCA diagnosis	Ongoing specific treatment

STUDY : CHUGAI-ARTEMIS - Edition date: DDMMYY

Pgm : DESCRIDEMO.SAS

Table 35 - Descriptive analysis – Administration of treatments at/after diagnosis of GCA - Analysis population (N=XX)

Parameter	Statistics	Total (N=XX)
Patients taking at least one treatment of Antiplatelets No Yes	n(%) n(%) Filled, n(%) Missing, n(%)	
Patients taking at least one treatment of Statins No Yes	n(%) n(%) Filled, n(%) Missing, n(%)	
Patients taking at least one treatment of Antiosteoporotic No Yes	n(%) n(%) Filled, n(%) Missing, n(%)	
Patients taking at least one treatment of Antihypertensives No Yes	n(%) n(%) Filled, n(%) Missing, n(%)	

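### Table 34 and its pre-diagnosis version leave out conditions judged aggravated by glucocorticoids, so pre-diagnosis comorbidity is understated and no planned table gives overall comorbidity regardless of attribution

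*SAP*

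**What the plan says.** **Protocol.** Section 6.2 lists the significant past and current comorbidities of patients as an endpoint of the patient-characteristics objective. Comorbidities related to GCs are a separate endpoint under another objective. Section 7.2.3.2 analyses the former without restriction: "Current and past comorbidities of GCA patients (significant past and concomitant diseases) will be coded". Section 5.3.1 defines GC-related comorbidities as those "which appeared or worsened during GCs treatment according to the investigator judgement", so the group includes old disease that got worse as well as new disease.

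**SAP.** Section 5.5.4.2 opens the comorbidity item with "Significant medical and surgical history and comorbidities (excluding those related / aggravated by the use of glucocorticoids", and the same parenthesis also removes GCA complications. Three descriptions sit beneath it: overall, "Significant medical and surgical history and comorbidities presented before the GCA (HORTON) diagnosis", and conditions with ongoing specific treatment. The Table 34 title repeats the restriction: "excluding those related to the use of GCs and complications related to GCA) overall by MedDRA SOC and PT". The pre-diagnosis version is a repeat of that shell: "The same table will be presented for significant medical and surgical history and comorbidities presented before the GCA (Horton) diagnosis". Listing 12 is restricted in the same way.

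The removed conditions are shown elsewhere. GC-related and GC-aggravated ones are in Table 12 ("Comorbidities related/ aggravated by the use of GCs according to the" investigator's judgment), and GCA complications are in Tables 20 and 21 ("Complications related to GCA according to the" investigator's judgment). SAP 5.6 declares one departure from the protocol, on treatments for GC-related comorbidities. It does not mention the exclusion.

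**The concern.** A table of what patients had before GCA should depend on when a condition began. Here it also depends on what happened later, because a later judgment that GCs worsened the condition takes it out. The loss runs in one direction and falls on the conditions that GCs worsen, which are of particular interest in this study.

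The second loss is the overall picture. Protocol section 1 gives limited comorbidity data, available only as proxies, as a weakness of the database study that preceded this one. With comorbidities divided by attribution and never recombined, the report would give no overall prevalence for at least one significant condition or for an organ class.

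**Working it through.** The plan states no figure that depends on these table definitions, so there is nothing to reproduce. The check traces one case through the tables, asks what can be recovered from them, and then illustrates the size.

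**1. Tracing one case.** Take a patient whose hypertension began years before GCA and which the investigator judges to have worsened on GCs.

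| Output | Hypertension counted? | Reason |
|---|---|---|
| Table 34, overall | No | GC-aggravated conditions excluded |
| Table 34, present before diagnosis | No | Same shell, same exclusion |
| Table 34, ongoing treatment | No | Same shell, same exclusion |
| Table 12 | Yes | Shown without onset before or after diagnosis |
| Table 21 | No | GCA complications only |

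This assumes that the condition is one CRF record carrying the GC judgment.

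**2. What can be recovered.**
- *Single preferred term, any time.* If each condition is recorded once per patient, the total is approximately the sum of that row in Tables 34, 12 and 21.
- *At least one condition, or an organ class.* Not recoverable, because a patient can be counted in more than one table. For two tables showing proportions a and b, the combined proportion lies between max(a, b) and min(1, a + b). With hypothetical values of 60% in Table 34 and 30% in Table 12, it lies anywhere from 60% to 90%.
- *Pre-diagnosis prevalence.* Not recoverable for any term with GC-aggravated cases, because Table 12 has no onset split.

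**3. Illustration of size.** Inputs:
- p, true pre-diagnosis prevalence: *assumed* equal to the database proxies in protocol section 1 (hypertension 74.3%, depression/insomnia 39.4%, osteoporosis 33.6%);
- f, share of pre-existing cases judged aggravated: *assumed* 10%, 20% or 40%, as the documents give no value;
- N = 300, protocol 4.2.

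Shown prevalence = p × (1 − f). Points lost = p × f.

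| Condition | p | f = 10% | f = 20% | f = 40% |
|---|---|---|---|---|
| Hypertension | 74.3% | 66.9% | 59.4% | 44.6% |
| Depression/insomnia | 39.4% | 35.5% | 31.5% | 23.6% |
| Osteoporosis | 33.6% | 30.2% | 26.9% | 20.2% |

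For hypertension the loss is 7.4, 14.9 or 29.7 points. In patients, 300 × 0.743 × f gives about 22, 45 or 89.

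For scale, the 95% half-width at the shown 66.9% is 1.96 × √(0.669 × 0.331 / 300) = 5.3 points. Under these assumptions the smallest hypertension loss already exceeds sampling error. For osteoporosis at f = 10% the loss is 3.4 points against a half-width of 5.2, so it does not.

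**The case against.** **Nothing disappears from the report.** A reader might infer that GC-aggravated conditions are lost altogether. They are not: Table 12 shows them by organ class and preferred term, and the Table 34 title states its exclusion openly. This limits the point to Table 34 and its repeats. It does not repair the pre-diagnosis version or supply the missing overall rate.

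**Table 12 follows the protocol.** A reader might infer that pooling new and worsened disease gives a wrong answer to the GC objective. The protocol defines GC-related comorbidity in just that way, so Table 12 answers the objective as written. Nor can one say how much of it is old disease. For hypertension, if 40% of the remaining 25.7% were new onset (10.3 points) and 10% of existing cases were aggravated, the old share is 7.4 / (7.4 + 10.3) = 42%. With 20% new onset (5.1 points) and 40% aggravated, it is 29.7 / (29.7 + 5.1) = 85%.

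**The protocol does not ask for a pre-diagnosis table.** True: the SAP added it, and the protocol already treats general and GC-related comorbidities as separate items. But a planned table should show what its title says, and the protocol's general endpoint is unrestricted.

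**Comparison with outside data.** A reader might infer that the literature comparison in protocol 9.1.2 becomes impossible. That section names neither comorbidities nor the database study. Table 35 and its repeats give antihypertensive, antiosteoporotic, antidepressant and hypnotic use with no GC exclusion, a partial counterpart to proxies built from diagnosis codes or treatments.

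**The CRF is not available.** If a worsened condition is entered twice, once as history and once as GC-related, the loss shrinks or may not occur. The SAP does not say which applies, so this objection stands as a limit on size.

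**Conclusion.** The point holds for Table 34 and its pre-diagnosis and ongoing-treatment repeats. On the text, the pre-diagnosis table understates the conditions that GCs worsen. No planned table gives all-attribution prevalence for at least one condition or by organ class, as the unrestricted endpoint in protocol 6.2 and 7.2.3.2 calls for. SAP 5.6 does not declare the change.

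The direction is clear but the size is not known. The fall from 74.3% to between 66.9% and 44.6% is an illustration, not an estimate. The aggravated share is assumed, and 74.3% is a proxy from another sample that the protocol does not present as a pre-diagnosis prevalence. The effect should be small in incident patients, diagnosed at most 6 weeks before inclusion, and larger in prevalent patients; the mix of the two is unknown. It would be smaller if worsened conditions are recorded twice. The primary objective is not affected.

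**What to change.** In SAP 5.5.4.2 and Table 34:

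1. Add an overall table of all significant comorbidities by organ class and preferred term, regardless of attribution, with the rate for at least one condition.
2. Remove the GC exclusion from the version for conditions present before GCA diagnosis.
3. Keep the current Table 34 as a supplement if wanted, and declare any retained exclusion in SAP 5.6.

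Optionally, where start dates allow, split Table 12 into new-onset and pre-existing-but-aggravated conditions. This is a refinement. Protocol 5.3.1 plans comorbidity start dates, but the field for presence before diagnosis is shown only in Listing 12, which leaves out GC-related conditions. Its availability for Table 12 should be checked first.

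When making the change, state whether a worsened condition is one CRF record or two, so that the new table counts each patient once per term.

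The cost is SAP wording, one or two extra table runs and slightly longer output.

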5.6 Changes from protocol

Current and past treatments used for comorbidities related to GCs will not be described as mentioned in the protocol regarding to the modifications of the CRF from version 1.2 to version 3.0 according to sponsor's decision. Indeed the dedicated table for specific treatments for comorbidities related to GCs was deleted.

This listing will include all treatments taken by patients with comorbidities related/aggravated by the use of glucocorticoids according to investigator's judgment.

6 INTERIM ANALYSIS

Not applicable

7 COMPUTER SYSTEMS, SOFTWARE AND VALIDATION OF PROGRAMS

7.1 Hardware

The statistical analysis will be performed using Windows 7 professional and a 64-bit operating system.

7.2 Software

All tables, listings and figures will be produced and statistical analysis performed using SAS® version 9.3 or above. All outputs will be edited in Microsoft Word Format.

7.3 Validation of programs

Validations will be done according to the procedure of the CRO ITEC Services.

The program reviewer is responsible for reviewing each project program and output provided to the sponsor. Program logs are reviewed for logical, syntax and fatal errors. The review in SAS® includes, but is not limited to, all ERRORS, WARNINGS, BY-VALUE merge messages, NOTES, and UNINITIALIZED variables. Program logs are also reviewed for accurate and consistent variable and observation counts following each procedure and data step.

The reviewing statistician is responsible for checking and reviewing the work produced using whatever method he/she feels is appropriate (e.g., SAS® code review, hand calculation, etc.) to reassure of the quality of the output.

Outputs are reviewed for typographical errors, misspellings and nonsensical values or results and to check the consistency with the statistical and analysis plan. Outputs are cross-checked against each other for accuracy and consistency. For statistical tables, listings, appendix listings, and figures, this procedure includes comparison of subject group numbers, counts of subjects at each observation point, and consistency of results for variables between outputs.

Findings of the quality control reviews are communicated to the party responsible for making necessary changes. The programs will be retested after modifications.

After final review, and when no further changes are required to produce the deliverable, the program reviewer and the statistician in charge of the study need to complete and sign a validation checklist, to indicate that they have successfully performed all of their responsibilities.

Copies of the internal quality control forms produced for the validation process and the sign-off forms will be provided to the sponsor to support the validation if asked.

